# 8.3 Study Schedule

Visit	Screening visit	Enrollment visit	Treatment start visit (Ts)	Follow-up visits (Tx - e.g. T1, T2 etc.)	Final visit (T F )
Timepoint			Day 0	T s + every 4-6 weeks during a 2-8 months period	Ts + 8 months
Informed Consent	Х				
Subject eligibility	Х	X4			
Demography	Х				
Medical history 	Х				
Concomitant medications	Х		Х	х	Х
Oral examination	Х				
X-ray 	Х				Х
Clinical photography3	Х			Х	Х
Intraoral scan	Х				Х
Intraoral refinement scan				X5	
Treatment plan (.stl- file) 		Х			
Subject questionnaire				Х	Х
Investigator questionnaire					Х
Aligners provided			Х	Х	
Aligner instructions to subject			Х		
AE/DD collection			Х	Х	Х

 Relevant medical conditions.

 Treatment screening X-ray and Treatment final X-ray (e.g. (PAN, CBCT, CEPH, and/or FMX).

 Intraoral and extraoral photographs.

 Treatment plan generated through Byte portal (final eligibility verification).

 Refinement scan only applicable if deemed needed by the investigtor.

- 8.3.1 Once aligners are manufacturered, the first fifteen (15) aligner stages will be provided to the Investigator. Additional aligner stages in sets up to fifteen (15) are provided to the Investigator to continue treatment after completion of the first fifteen (15) sets.
- 8.3.2 The Investigator will provide the subject with aligners at treatment start and at monthly check-ins with the Investigator at clinic visits.
- 8.3.3 Once the aligner trays are received by the subject, they can start their treatment. The date the aligners are received will be recorded as the start date of each subject's participation (TS). The initial visit worksheet must be completed at this time.
- 8.3.4 The subject visits will be performed monthly (every 4-6 weeks). The Investigator will review the subject's treatment progress, confirm treatment plan and follow-up on any safety events. A visit worksheet must be completed at each visit (T1, T2, T3, etc.).

**CONFIDENTIAL:** The information in this study protocol is strictly confidential and is available for review to Investigators, study center personnel, the ethics committee, and the health authorities. It will not be disclosed to third parties without written authorization from the Sponsor, except to obtain informed consent from persons receiving the study treatment. Once the protocol is signed, its terms are binding for all parties.

- 8.3.5 The study aims to collect the following data at the following time points:
  - Intraoral scans of the subject prior to the start of treatment (Ts) and end of treatment (TF).
  - X-ray (PAN, CBCT, CEPH, and/or FMX) prior to the start of treatment (Ts) and at the end of treatment final visit (TF).
  - Intraoral and extraoral photographs prior to the start of treatment (Ts), at every check-in visit, and end of treatment final visit (TF).
  - Completed visit worksheet at initial aligner visit (TS), scheduled monthly check in visits (4-6 week intervals: T1, T2, T3, T4, etc.), and final aligner visit (TF).
  - Completed subject questionnaire at check in visits (4-6 week intervals: T1, T2, T3, T4, etc.),
  - Subject post-treatment questionnaire at the end of the treatment (TF).
  - Relevant medical conditions and concomitant medication incl. trade name, dosage, route and start.
  - AE/DD documentation
- 8.3.6 At the final aligner treatment visit  $(T_F)$ , the dentist will complete a final visit worksheet and subject will complete the post-treatment questionnaire.
- 8.3.7 Each subject will receive removable retainers following completion of aligner therapy.

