#### 4.3 Study Duration

- 4.3.1 The study, as a whole is expected to run for up to 18 months, inclusive of the enrollment period.
- 4.3.2 The minimum planned orthodontic treatment period per subject will be 2 months.
- 4.3.3 The maximum planned orthodontic treatment period per subject will be 8 months, unless a refinement is required.
- 4.3.4 Study subjects will remain on-study until treatment with the final investigational or control device is complete or if the subject wishes to no longer participate in the study (withdraws consent) or Severe non-compliance to protocol as judged by the Investigator and/or Sponsor causing the subject to be withdrawn from the study.

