# 8.9 Treatment Final

- 8.9.1 The following will be collected at final treatment visit (TF).
  - Intraoral scan
  - X-ray (CBCT, CEPH, PAN, and/or FMX)
  - Intraoral and extraoral photographs
  - Final visit worksheet (TF)
  - Post-treatment subject questionnaire
- 8.9.2 Each subject will receive removable retainers following completion of aligner therapy.
- 8.9.3 Participation in this study ends for each subject when:
  - Subjects complete treatment with the investigational or control device and the Investigator determine that a retainer can be ordered.

- When a subject withdraws their consent to continue participating in the study.
- If an Investigator removes a subject from the study due to ineligibility or non-compliance with study protocols.

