# 9.3 **Primary Efficacy Endpoint**

The primary effectiveness endpoint is the comparison between the treatment groups of the quantification of actual vs planned tooth movements using weighted Peer Assessment Rating (PAR) index.

• Planned percentage reduction in PAR Score (Planned Improvement of Malocclusion [PIM])

In addition comparison between treatment groups will also be performed for:

- Actual percentage reduction in PAR Score (Actual Improvement of Malocclusion [AIM])
- Percentage of Accuracy of Outcome

Quantification and comparison of expressed and programmed tooth movements will be conducted using to measure orthodontic treatment need and outcome, the built-in weighted PAR analysis tool of 3Shape Ortho System software (K152086).

- 9.3.1 The weighted PAR scores for each Digital Study Model (DSM) would be compared as follows:
  - Planned percentage reduction in PAR Score (Planned Improvement of Malocclusion [PIM]) = PAR Score TS- PAR Score TP / PAR Score TS \* 100
  - Actual percentage reduction in PAR Score (Actual Improvement of Malocclusion [AIM]) = PAR Score TS- PAR Score TF / PAR Score TS \* 100
  - Percentage of Accuracy of Outcome = 100% [(|PIM -AIM|/|AIM|) \*100%]

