#### 12.2 Data Analysis

- 12.2.1 The Sponsor and Investigators are not blinded to the study data during the conduct of the trial, and may at periodic intervals analyze the data to assess study progress.
- 12.2.2 If nothing else is stated, descriptive statistics will be given for each variable in the clinical study and p-values may be complemented by confidence intervals as appropriate. When using the terminology descriptive statistics, it is meant that the number of subjects (N), mean, median, standard deviation (Sd), minimum (Min) and maximum (Max) values will be presented for continuous data and frequencies and percentages for categorical data.

- 12.2.3 All tooth movement data analyses will be performed using 3Shape Ortho System (K152086).
- 12.2.4 Three .stl files from each subject would be used for the analysis:
  - A pre-treatment STL file (TS) would be generated by scanning subject's pre-treatment intraoral scan taken before the start of treatment.
  - A planned or programmed STL (TP) file would be obtained from Archform Orthodontic Software System (K213916) after planned or programmed tooth movements have been made based on the treatment plan finalized by the digital lab and study Investigators.
  - The actual post-treatment STL file (TF) would be generated by scanning subject's post-treatment intraoral scan at the end of treatment.
- 12.2.5 Each STL file would convert into a Digital Study Model within the 3Shape Ortho System software to standardize the analysis.
- 12.2.6 Each DSM would be segmented using the "auto segmentation tool" of the software to demarcate each tooth separately.
- 12.2.7 This would be followed by Peer Assessment Rating (PAR) index to measure orthodontic treatment need and outcome (Richmond, 1992). This would be done using the built-in weighted PAR analysis tool of 3Shape Ortho System software. The PAR index will be performed by an external evaluator.
- 12.2.8 The weightage for each component of the PAR index would be set as: maxillary and mandibular anterior segment alignment x 1; buccal occlusion x 1; overjet x 6; overbite x 2; centerline x 4; following the ABO guidelines. The weighted PAR scores for each DSM would be compared as follows:

The PAR Score values for  $T_S$ ,  $T_P$ , and  $T_F$  will be transferred to the eCRF and the following will be calculated:

- Planned percentage reduction in PAR Score (Planned Improvement of Malocclusion [PIM]) = PAR Score TS- PAR Score TP / PAR Score TS \* 100

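### The schedule table fixes the final visit (TF) at 8 months after treatment start, while the text and the endpoint derivation place TF at the end of treatment

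*Combined protocol and SAP*

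**What the plan says.** The Timepoint row of the table in section 8.3 reads, across the follow-up and final-visit columns, "T s + every 4-6 weeks during a 2-8 months period Ts + 8 months". The follow-up column therefore covers a variable span, while the final visit has one fixed time with no window and no alternative. The final visit holds the only intraoral scan after screening, apart from an optional refinement scan during follow-up.

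The text treats TF differently. Section 12.2.4 states: "The actual post-treatment STL file (TF) would be generated by scanning subject's post-treatment intraoral scan at the end of treatment". Section 8.3.5 also ties the TF scan to the end of treatment, and 8.9.1 lists it among the items collected at the final treatment visit.

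Treatment length varies between subjects. Section 4.3.2 sets a planned minimum of 2 months, and 4.3.3 adds: "The maximum planned orthodontic treatment period per subject will be 8 months, unless a refinement is required". The synopsis gives 6 to 8 months as typical. Section 4 closes a subject's study period when device use stops. Section 8.9.3 ends participation when, among other events, "Subjects complete treatment with the investigational or control device and the Investigator determine that a retainer can be ordered". Retainers follow completion of aligner therapy (sections 4, 8.3.7 and 8.9.2).

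The TF score enters the outcome through section 9.3: "Actual percentage reduction in PAR Score (Actual Improvement of Malocclusion [AIM]) = PAR Score TS- PAR Score TF / PAR Score TS", multiplied by 100. Accuracy of Outcome is then computed from PIM and AIM.

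**The concern.** TF is both a visit that sites must book and the tooth position that the analysis treats as achieved. If the booking rule and the analytic definition differ, the scan may not show the state that the analysis assumes.

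Under the table, a subject who finishes early is scanned after a period in retainers, so AIM and Accuracy would combine the treatment result with whatever happened during retention. A subject whose refinement continues past month 8 would be scanned before treatment is complete. With up to 15 sites, some could follow the table and others the text, and a scan taken at the wrong time cannot be retaken later. The final questionnaires are scheduled at the same visit and would move with it, although section 9.4 asks for satisfaction when treatment is completed.

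**Working it through.** **Plan's own figure.** The only computed design figure is 23 evaluable subjects per arm (section 12.1.2). With SD 1, difference 1, two-sided alpha 0.05 and power 0.90, the two-sample t-test needs 22.02 per arm, rounded up to 23, where power is 0.912. The figure reproduces, and scan timing does not alter it.

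**Step 1: gap between end of treatment and scan under the table.** Gap = 8 months − treatment length. A negative value means that the scan precedes completion.

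| Treatment length (months) | Source | Gap (months) |
|---|---|---|
| 2 | 4.3.2, planned minimum | 8 − 2 = 6 |
| 4 | illustration within the planned range | 8 − 4 = 4 |
| 6 | synopsis, lower typical value | 8 − 6 = 2 |
| 8 | 4.3.3, planned maximum; upper typical value | 8 − 8 = 0 |
| 9 | assumed, refined course | 8 − 9 = −1 |
| 10 | assumed, refined course | 8 − 10 = −2 |
| 12 | assumed, refined course | 8 − 12 = −4 |

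The last three lengths are assumptions, because the protocol sets no upper limit on a refined course. Under the definition in 12.2.4 the gap is 0 for everyone, subject to whatever visit window is set.

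**Step 2: which measures move.** PIM uses the TS and TP scores only, so it does not depend on TF. AIM = (PAR at TS − PAR at TF) / PAR at TS × 100 does. Accuracy depends on TF through AIM.

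**Step 3: could the gap differ between arms?** Section 6.1 describes a 20% difference in planned movement rate, but the per-aligner limits in its two tables differ for only some movements. The ratio of Daytime to Nighttime limits, which is the ratio of Nighttime to Daytime tray counts for the same total movement, is:

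- translation: 0.3 / 0.25 = 1.20
- rotation: 2 / 1.6 = 1.25
- torque: 1 / 1 = 1.00
- tip: 1 / 1 = 1.00
- intrusion: 0.1 / 0.1 = 1.00

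At equal tray intervals, Nighttime treatment therefore lasts 1.00 to 1.25 times as long, depending on which movement limits the plan.

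| Daytime length (months) | Daytime gap | Nighttime gap at ×1.00 | at ×1.20 | at ×1.25 | Difference between arms |
|---|---|---|---|---|---|
| 2 | 6 | 6 | 8 − 2.4 = 5.6 | 8 − 2.5 = 5.5 | 0 to 0.5 |
| 4 | 4 | 4 | 8 − 4.8 = 3.2 | 8 − 5.0 = 3.0 | 0 to 1.0 |
| 6 | 2 | 2 | 8 − 7.2 = 0.8 | 8 − 7.5 = 0.5 | 0 to 1.5 |

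Both arms may wear each tray for 1 to 2 weeks or as the dentist instructs. That twofold latitude is larger than the greatest ratio above, so the equal-interval assumption may not hold.

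**Step 4: effect on PAR.** The documents give no relapse rate and no rate of PAR change late in treatment. The gaps in months cannot be converted into PAR points.

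**The case against.** The strongest reply is that the document as a whole already settles what TF means. Sections 8.3.5, 8.9 and 12.2.4, and the effectiveness assessment in the synopsis, all point to the end of treatment. Sections 4, 4.3.4 and 8.9.3 end the study for a subject at that point, so a site could scan a 2-month finisher at month 8 only by overriding them. The neighbouring table cell, "every 4-6 weeks during a 2-8 months period", expects variable duration, and 8 months is also the planned maximum. Month 8 may therefore have been meant as a nominal upper limit.

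Much of this stands, and it limits the point to a contradiction in one table cell. It does not remove it. No section says that month 8 is nominal or a maximum for the visit, and the table is the natural place for a site to look when booking.

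Four stronger readings are tempting, and the documents do not support them:

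- **The arms are scanned at systematically different times.** The 1.0 to 1.5 month difference for 4 to 6 month control courses is the top of a range that starts at zero. Torque, tip and intrusion limits are identical in the two arms, and tray wear may vary in either.
- **Refined cases are scanned mid-treatment.** This holds only where refinement runs past month 8. A short plan with a refinement can finish before then.
- **The treatment-duration correlations in 12.2.10 collapse to a constant.** No section defines duration as TS to TF.
- **Every efficacy result is compromised.** PIM, which section 9.3 lists first under the primary endpoint, does not use TF. AIM and Accuracy are not the only outcomes either: satisfaction, pain and comfort are also measured.

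**Conclusion.** The contradiction is real and should be corrected. The table's fixed time and the text's end of treatment coincide only for a subject whose treatment ends at month 8. If a site follows the table, the scan behind AIM and Accuracy comes 0 to 2 months after treatment for typical courses and 6 months after at the planned minimum, when participation has ended and retainers have been given. It comes before completion only for a refinement that runs past month 8.

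These sizes rest on the protocol's own treatment lengths and on a literal reading of the table. Any arm difference depends on the limiting movement and the tray interval, with a duration ratio from 1.00 to 1.25. Neither the direction nor the size of a bias in PAR points can be stated. The sample size is unaffected.

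**What to change.** Reconcile the passages so that TF has one definition. In the 8.3 table, replace the fixed month for the final visit with the definition that the protocol already uses in 8.3.5 and 12.2.4, namely end of aligner treatment including any refinement. Add a short visit window in days, its length to be set by the sponsor.

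Record the date of the last aligner in the eCRF so that the interval to the TF scan can be checked for each subject and summarised by arm. State in 12.2 that out-of-window scans are flagged and examined in a sensitivity analysis of AIM and Accuracy.

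The cost is one table cell, one sentence on the window, one on the sensitivity analysis and one date field. The small downside is that final visits must be booked to each subject's completion and not to a common calendar month.

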# 8.4 Subject Eligibility

8.4.1 Subject Eligibility, informed consent, and if applicable parental consent shall be documented and later transferred to the **eCRF**.

# 8.5 Subject Information

8.5.1 Subject demographic information including subject ID, age, gender, ethnicity and race will be collected and transferred to the corresponding **eCRF**.

# 8.6 **Pre-Treatment Period**

- 8.6.1 The following will be collected prior to aligner treatment, and are required for the treatment planning phase of aligner therapy:
  - Intraoral scan
  - X-ray (CBCT, CEPH, PAN and/or FMX)
  - Intraoral and extraoral photographs

# 8.7 Treatment Start

- 8.7.1 The initial delivery of the investigational or control devices will be received by the subject (TS). A visit worksheet is required for the initial aligner visit. Visit worksheet data will be transferred to the eCRF.
  - The subject will be directed on use and care of the investigational or control device during the treatment period.

## 8.8 In-Treatment Period

- 8.8.1 The subject will check in with the Investigator at their dental practice/office monthly (every 4-6 weeks).
  - The Investigator will review the subject's treatment progress and provide feedback to the subject and the Sponsor related to compliance and tracking via completion of a visit worksheet at each visit (T1, T2, T3, etc.).
  - The Investigator will also take subject progress intraoral and extraoral photographs at each check in visit and submit them to the Sponsor.
  - In-treatment subject questionnaire
- 8.8.2 The Investigators and the Sponsor will assess the progression of investigational treatment through information subject submitted to the **eCRF**.

# 8.9 Treatment Final

- 8.9.1 The following will be collected at final treatment visit (TF).
  - Intraoral scan
  - X-ray (CBCT, CEPH, PAN, and/or FMX)
  - Intraoral and extraoral photographs
  - Final visit worksheet (TF)
  - Post-treatment subject questionnaire
- 8.9.2 Each subject will receive removable retainers following completion of aligner therapy.
- 8.9.3 Participation in this study ends for each subject when:
  - Subjects complete treatment with the investigational or control device and the Investigator determine that a retainer can be ordered.

- When a subject withdraws their consent to continue participating in the study.
- If an Investigator removes a subject from the study due to ineligibility or non-compliance with study protocols.

#### 8.10 Subject Discontinuation

- 8.10.1 The Investigator and/or the Sponsor may discontinuing a subject if severe non-compliance to the protocol. Subject may also be discontinued due to safety reasons as judged by the Investigator and/or Sponsor.
- 8.10.2 If a subject for any reason desires to no longer participate in the study or continue treatment, they are free to discontinue participation in the study, at any time and without providing a reason for the withdrawal. Discontinuation from the clinical study will not affect future treatment /care of the subject.
- 8.10.3 Subjects who discontinue should always be inquired about the reason(s) for their discontinuation and any potential safety issues. If possible, they should be seen and assessed by an Investigator. The termination section in the eCRF should be completed. Safety events should be followed up. Any study specific material provided to the subject should be collected.

#### 9. ENDPOINTS

# 9.1 **Primary Safety Endpoint**

The primary safety endpoint of the study will be the incidence of (device or dental) related AEs and SAEs associated with the planned investigational treatment, compared to the incidence from treatment with the control device.

#### 9.2 Secondary Safety Endpoint

The secondary safety endpoint of the study will be the subject self-reported values pertaining to pain/discomfort during treatment and comfort in wearing the aligners captured in the questionnaire. For this endpoint, a Visual Analogue Scale (VAS) with a Wong Baker face scale is used.

- 9.2.1 Subject comfort wearing aligners during treatment via visual analogue scales (VAS): This question is directed to the subject. "How comfortable were the aligners to wear during your treatment?" (VAS: 0 very comfortable 10 very uncomfortable).
- 9.2.2 Subject pain associated with new tooth movements during treatment via visual analogue scales (VAS): This question is directed to the subject.
  "Did you experience any pain associated with new tooth movement?" (VAS: 0 no pain 10 worst possible pain).

**CONFIDENTIAL:** The information in this study protocol is strictly confidential and is available for review to Investigators, study center personnel, the ethics committee, and the health authorities. It will not be disclosed to third parties without written authorization from the Sponsor, except to obtain informed consent from persons receiving the study treatment. Once the protocol is signed, its terms are binding for all parties.

# 9.3 **Primary Efficacy Endpoint**

The primary effectiveness endpoint is the comparison between the treatment groups of the quantification of actual vs planned tooth movements using weighted Peer Assessment Rating (PAR) index.

• Planned percentage reduction in PAR Score (Planned Improvement of Malocclusion [PIM])

In addition comparison between treatment groups will also be performed for:

- Actual percentage reduction in PAR Score (Actual Improvement of Malocclusion [AIM])
- Percentage of Accuracy of Outcome

Quantification and comparison of expressed and programmed tooth movements will be conducted using to measure orthodontic treatment need and outcome, the built-in weighted PAR analysis tool of 3Shape Ortho System software (K152086).

- 9.3.1 The weighted PAR scores for each Digital Study Model (DSM) would be compared as follows:
  - Planned percentage reduction in PAR Score (Planned Improvement of Malocclusion [PIM]) = PAR Score TS- PAR Score TP / PAR Score TS \* 100
  - Actual percentage reduction in PAR Score (Actual Improvement of Malocclusion [AIM]) = PAR Score TS- PAR Score TF / PAR Score TS \* 100
  - Percentage of Accuracy of Outcome = 100% [(|PIM -AIM|/|AIM|) \*100%]

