EFFECTIVENESS ASSESSMENTS	Efficacy of Nighttime Aligners (worn 10-12 hours per day or night) will be assessed by demonstrating no statistically significant difference between expressed tooth movement versus programmed tooth movement at the end of treatment when compared to the Daytime aligners (worn 20-22 hours day/night). Quantification and comparison of expressed and programmed tooth movements will be conducted using Peer Assessment Rating (PAR) index to measure orthodontic treatment need and outcome, using the built-in weighted PAR analysis tool of 3Shape Ortho System software.
SAFETY ASSESSMENTS	The primary safety endpoint of the study will be the incidence of (device or dental) related AEs associated with the planned investigational treatment, as well as the occurrence of SAEs. Additionally, safety will be assessed through a post-treatment questionnaire administered to the subject asking about subject perceived comfort during treatment. Results will be quantified using a visual analogue scale. Both numerical values and a Wong Baker face scale will be used.
INCLUSION CRITERIA	
 
For inclusion in this clinical study subjects must meet all of the following criteria: 
 
Subject willing to participate in the clinical study and able to understand the content of the clinical study.
 
 
 
Subject must have permanent dentition (i.e. all second molars).
 
Subject must be 12 years of age or older.
 
Subject must be able to provide and sign consent for themselves, without requiring consent to be given by a legally authorized representative. Parental consent is also required for all participants who are not of the legal age to provide consent themselves (based on participant state of residence).
 
The subject requires correction of teeth without planned extrusive movements on either or both arches.
 

	
 
The subject has no greater than 5 mm of crowding and/or spacing (based on estimation by Investigator).
 

	
 
The subject does not require planned correction of molar tooth positions, posterior bite or molar classic relationship corrections. Subjects with Class II or Class III malocclusions requiring posterior bite / class correction are not eligible.
 

	
 
Subjects without prior orthodontic treatment within the past 18 months.
 

	9. Subjects who are periodontally stable.
	10. Subjects without a known history of plastic allergies.

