# 1. STUDY OBJECTIVES

# 1.1 **Primary Objective:**

The primary efficacy objective of this study is the comparison between groups of the quantification of actual vs planned tooth movements. Changes in tooth position from pre-treatment baseline to end of treatment results will be measured for both Daytime Aligners (control) and Nighttime Aligners (test).

The safety objective of the study will be the incidence of (device or dental) related AEs associated with the planned investigational treatment, in comparison to the incidence of AEs associated with control treatment.

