- Actual percentage reduction in PAR Score (Actual Improvement of Malocclusion [AIM]) = PAR Score TS- PAR Score TF / PAR Score TS \* 100
- Percentage of Accuracy of Outcome = 100% [(|PIM AIM|/|AIM|) \*100%]

Statistical analysis comparing the two treatment groups using the Wilcoxon rank sum test will pe performed. A two-sided p-value below

5% will be regarded as statistically significant. The null hypothesis of the study is that there is no difference between the two groups.

- 12.2.9 Additional comparisons between treatment groups may be performed and p-values presented using the Wilcoxon rank sum test. Wilcoxon signed rank test may be used for analysis within treatment groups over time.
- 12.2.10 Calculation of Spearman's rank correlation coefficients will be performed to elucidate the relationships between the accuracy of outcome with treatment duration, number of aligners, subject pain levels, and overall subject and doctor satisfaction for each group.
- 12.2.11 All methods used in this clinical study have been previously published and reviewed (Griffith 2021, Grünheid 2022). All data in this clinical study will be analyzed by an independent contractor to remove bias. Any adjustments or modifications to these methods will be duly documented and reported.

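### Section 9.3 words the primary efficacy endpoint as actual versus planned movement, but the one measure listed under it (PIM) contains no end-of-treatment data

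*Combined protocol and SAP*

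**What the plan says.** Section 9.3 opens by defining the primary effectiveness endpoint as "the comparison between the treatment groups of the quantification of actual vs planned tooth movements", measured by the weighted PAR index. One bullet follows: "Planned percentage reduction in PAR Score (Planned Improvement of Malocclusion [PIM". A new sentence, "In addition comparison between treatment groups will also be performed for", then introduces AIM (the actual percentage reduction) and the Percentage of Accuracy of Outcome.

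Two other places describe the aim:

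- Section 1.1: "The primary efficacy objective of this study is the comparison between groups of the quantification of actual vs planned tooth movements", with change measured from baseline to end of treatment.
- Synopsis, effectiveness assessments: efficacy is to be shown by "no statistically significant difference between expressed tooth movement versus programmed tooth movement at the end of treatment", relative to the Daytime arm.

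Section 12.2.4 gives the sources of the three models. TS is the pre-treatment scan and TF the end-of-treatment scan. For the third, "A planned or programmed STL (TP) file would be obtained from Archform Orthodontic Software System (K213916". The schedule in 8.3 places the treatment plan at the enrollment visit, before Day 0, and its footnote reads "Treatment plan generated through Byte portal (final eligibility verification".

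Section 12.2.8 repeats the three formulas and then says "Statistical analysis comparing the two treatment groups using the Wilcoxon rank sum test will pe performed", without naming the variable to be tested. Section 12.1.2 gives a standard deviation of 1 and a difference of 1, again without saying of what.

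**The concern.** The lead sentence of 9.3 and the measure beneath it describe different things. A comparison of actual with planned movement needs the final scan, and PIM does not use it. If the listed measure is followed, the primary test asks only whether the two arms were planned alike.

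That can mislead in two directions.

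- **Arms planned alike.** The test will usually be non-significant however poorly the teeth moved, and the synopsis treats a non-significant difference as evidence of efficacy. The absence of an equivalence margin is a separate issue, but it makes this one more damaging.
- **Arms planned differently.** Section 4 says enrollment is on a convenience basis, and allocation is not described as random, so case mix or planning may differ between arms. A significant PIM difference would reflect that and not device performance.

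If PIM is not what was meant, the reader cannot tell which of the three results is primary. Section 12.2.1 leaves the sponsor and investigators unblinded and allows periodic analysis, so the choice could be made after results are known.

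**Working it through.** **The plan's own figure.** Section 12.1.2 gives 23 per arm for SD 1, difference 1, power 0.90 and two-sided alpha 0.05. A two-sample t-test requires 22.02 per arm, rounded up to 23; power is 0.900 at 22 and 0.912 at 23. The figure reproduces, but nothing ties the SD and the difference to PIM, AIM or Accuracy, so the calculation does not reveal the intended primary variable.

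**Formulas (9.3.1 and 12.2.8).** The numerators are read as bracketed, which is the only reading that gives a percentage reduction. A minus sign is assumed after 100% in the Accuracy formula, because none appears in the extracted text.

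- PIM = (TS − TP)/TS × 100
- AIM = (TS − TF)/TS × 100
- Accuracy = 100 − |PIM − AIM|/|AIM| × 100
- By subtraction, PIM − AIM = (TF − TP)/TS × 100

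PIM has no TF term, so it cannot respond to the result of treatment. This follows from the algebra and needs no assumption about the data.

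**Illustration with assumed scores TS = 20, TP = 4.** PIM = (20 − 4)/20 × 100 = 80% in every row.

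| TF | PIM | AIM | PIM − AIM | Accuracy, \|AIM\| denominator | Accuracy, \|PIM\| denominator |
|---|---|---|---|---|---|
| 4 | 80 | 80 | 0 | 100% | 100% |
| 12 | 80 | 40 | 40 | 0% | 50% |
| 16 | 80 | 20 | 60 | −200% | 25% |
| 20 | 80 | 0 | 80 | undefined | 0% |

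The first row is full expression of the plan and the last is no improvement at all. PIM does not separate them.

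**Both arms planned alike, efficacy varied.** Simulation under assumed score distributions, 23 per arm, 4,000 trials per setting, Wilcoxon rank sum at two-sided 5%. The Nighttime arm was set to express 100%, 75%, 50% or 25% of the control arm's movement.

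- PIM was significant in 4.8%, 4.7%, 5.3% and 5.0% of trials, which is simply alpha.
- AIM was significant in 4.6%, 99.4%, 100% and 100%.

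**Plans that differ between arms.** Same test, 23 per arm, normal data assumed, 20,000 trials per setting (Monte Carlo SE at most 0.004).

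| PIM imbalance (SD) | 0 | 0.25 | 0.5 | 0.75 | 1.0 |
|---|---|---|---|---|---|
| Proportion with p < 0.05 | 0.049 | 0.128 | 0.355 | 0.671 | 0.894 |

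These rates do not depend on efficacy, because TF is not in the variable.

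**The case against.** The best defense is to read 9.3 as a whole. All three measures sit under the primary endpoint heading, 9.3.1 defines all three, and 9.4 confines the secondary efficacy endpoint to satisfaction. Section 12.2.10 uses accuracy of outcome as the variable for its correlations. On that reading, PIM alone is the least likely intent, and the outcome data will be collected and compared anyway.

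This limits the harm, because AIM and Accuracy are not lost. It does not remove the contradiction. The linking sentence sets those two apart from PIM, and no section calls either of them primary. If all three were meant to be primary, there is no rule for results that disagree.

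Four narrower points:

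- **The imbalance rates rest on assumptions.** The documents give no PIM distribution, and PIM needs no final scan, so it could be available for up to 50 per arm. At 50 the rates rise to about 5%, 22%, 67%, 95% and 99.8%. The case against PIM rests on its formula, not on these rates.
- **Refinement could alter the plan.** The documents allow it and do not say which plan then supplies TP. A revised TP would still be a plan, not an outcome.
- **A final scan may be missing.** Section 12.2.4 expects three files from each subject, but the final scan is taken at the final visit and 8.10 does not require one at discontinuation. This stands: a TF-based primary endpoint needs a stated rule for missing TF.
- **PIM − AIM is signed.** Under- and over-expression can offset each other, whereas Accuracy uses an absolute discrepancy. This also stands as a trade-off for the sponsor to settle.

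**Conclusion.** The concern holds, and the text is wrong as written. The only measure placed directly under the primary endpoint sentence cannot answer the objective in 1.1, and no other section supplies a different primary variable. That conclusion rests on the formula and on the structure of 9.3, not on any data assumption.

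The numerical size depends on assumed scores and distributions. With similar planning in both arms, a PIM test is non-significant about 95% of the time whatever the device does. With unequal planning at 23 per arm, it is significant in about 13% of trials at a 0.25 SD imbalance and 89% at 1 SD, for reasons unrelated to performance.

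The defect is confined to what is designated primary. It must be fixed before results are examined, because it leaves open which of three results decides the trial.

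**What to change.** In 9.3 and 12.2.8, name one variable that uses TF as the single primary endpoint and state that the Wilcoxon rank sum test applies to it. One candidate is the per-subject difference PIM − AIM = (TF − TP)/TS × 100. It measures actual against planned directly, is defined when AIM is 0 and fits the specified test. If offsetting of under- and over-expression is unwanted, its absolute value can be used.

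Two alternatives need further changes:

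- **Accuracy of Outcome:** change the denominator from |AIM| to |PIM|, because the present form is undefined at AIM = 0.
- **AIM adjusted for PIM:** replace the Wilcoxon test with a regression (ANCOVA) model.

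In 12.1, state the SD and the difference for the chosen variable in its own units. Report PIM by arm as a baseline check that planning was comparable. State which plan supplies TP after a refinement, and how subjects without a final scan are handled.

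The cost is a protocol amendment to 9.3, 12.1 and 12.2.8. The restated inputs may change the 23 per arm. No new data collection is needed, because 12.2.8 already sends the TS, TP and TF scores to the eCRF.
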